## 1.0 Objectives

### 1.1 Study Objectives

Hypothesis: Patients on Angiotensin Converting Enzyme Inhibitors (ACEI) or Angiotensin Receptor Blockers (ARB) experience more profound hypotension upon anesthetic induction with propofol compared with methohexitol.

Specific Aim 1: To determine the incidence of hypotension during anesthetic induction with propofol and methohexitol in patients being chronically treated with ACEI or ARB.

Specific Aim 2: To determine the effect of propofol and methohexitol on circulating neurohormones relevant to hemodynamic homeostasis in this population, namely arginine vasopressin (AVP), Angiotensin II (All), norepinephrine (NE) and epinephrine (Epi).

### 1.2 Primary Study Endpoints

The primary endpoint of the study is episodes of hypotension in the 15 minutes following anesthetic induction with propofol versus methohexitol. Hypotension is defined as a drop in systolic blood pressure by 30% compared to baseline systolic blood pressure and/or systolic blood pressure less than 85 mmHg. One such episode is sufficient to qualify as intraoperative hypotension.

### 1.3 Secondary Study Endpoints

During the first 15 minutes following anesthetic induction:

- (1) The total number of doses of vasopressors (ephedrine, phenylephrine or vasopressin) administered
- (2) Duration of each hypotension episode
- (3) Refractory hypotension (defined as systolic blood pressure <85mm Hg following 3 doses of vasopressors)
- (4) Systolic blood pressure (at 1 minute intervals)
- (5) Diastolic blood pressure (at 1 minute intervals)
- (6) Heart rate (at 1 minute intervals)
- (7) Blood levels of AVP, All, Epi, NE (at 3, 5, 10 and 15 min)

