### **Both groups**

Following induction in both groups, the blood pressure and heart rate will be measured every one minute for the first 15minutes following the administration of either propofol or methohexitol, and all hemodynamic parameters (systolic blood pressure, diastolic blood pressure, heart rate) will be recorded on the data collection sheet.

Hypotension will be defined as a systolic blood pressure of less than 85 mmHg or greater than 30% decrease in the mean systolic blood pressure (as determined above), whichever is greater. If the patient develops hypotension with a systolic blood pressure of less than 85mm Hg during the 15 minutes following induction of anesthesia, the treatment algorithm outlined below will be followed (Eyraud et al., 1999; Mets, 2013):

One dose of phenylephrine will be administered if heart rate is 60 bpm or above, whereas 5mg of ephedrine will be administered if heart rate is below 60 bpm. The blood pressure will be rechecked 1 minute following, and the process repeated once or twice if necessary. If the

patient is still hypotensive following 3 total doses of vasopressors (phenylephrine and/or ephedrine), they will be considered to be in refractory hypotension and 0.5 Units of vasopressin will be administered. The blood pressure will be rechecked 1 minute following administration of vasopressin. If systolic blood pressure is still less than 85 mmHg, an additional 0.5 Units of vasopressin will be repeated once or twice as needed. Persistent refractory hypotension despite the aforementioned vasopressors will be treated with 4 micrograms of intravenous norepinephrine. All hemodynamic parameters for 15min following anesthetic induction will be recorded by the attending anesthesiologist.

Following anesthetic induction in both study groups, blood samples will be collected (as described above) at 3, 5, 10 and 15 minutes following anesthesia induction. The blood samples will be processed by dedicated research technician as described below.

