## 8.3 Statistical methods

Primary analyses will invoke an intent-to-treat paradigm, wherein all randomized subjects are included according to their randomized treatment arm, regardless of actual treatment received, compliance, etc. Data will be summarized using descriptive statistics for continuous variables (mean, standard deviation, number of observations, and percentiles) and frequency statistics (frequencies and percentages) for categorical variables. Univariate and bivariate distributions will be inspected in order to address any missing data, inconsistent responses, outliers, and data entry errors. The sample size estimates have taken into consideration a participant drop-out of 20%; however, every effort will be made during the studies to minimize any drop-out. All hypothesis tests will be two-sided and analyses will account for the two randomization stratification factors of gender and inhibitor type. All analyses will be performed using SAS software, version 9.4 (SAS Institute, Inc., Cary, NC), R software, version 3.2.2 (R Foundation for Statistical Computing, Vienna, Austria), or Stata software, version 13 (StataCorp LP, College Station, TX).

For the primary outcome of the proportion of participants having at least one hypotension episode, log-binomial regression will be used to compare the propofol and methohexitol groups, adjusting for the randomization stratification factors of gender and inhibitor type. Because this is a prospective study, the log-binomial model allows us to estimate the risk ratio rather than the odds ratio while adjusting for covariates (Wacholder, 1986).

For secondary outcome of the proportion of patients experiencing refractory hypotension, the log-binomial model as described for the primary outcome will be used to compare the treatment groups. Poisson regression will be used to compare the two treatment groups, adjusting for the randomization stratification factors, with respect to the secondary outcomes of (a) the number of vasopressor doses (i.e., ephedrine, phenylephrine and vasopressin) administered per patient and (b) the number of hypotension episodes per patient over the first 18 after treatment initiation. In the event that there is an excess of zero counts, zero-inflated Poisson (ZIP) regression will be considered (Lambert, 1992).

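### The vasopressor-dose endpoint omits norepinephrine, the last step of the protocol's own algorithm, so a patient who needs it scores the same as one controlled on the last vasopressin dose

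*Combined protocol and SAP*

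**What the plan says.** Section 1.3 sets the window for all secondary endpoints, "During the first 15 minutes following anesthetic induction", and lists as item (1) "The total number of doses of vasopressors (ephedrine, phenylephrine or vasopressin) administered". Section 8.3 plans a Poisson regression, adjusted for the stratification factors, of "the number of vasopressor doses (i.e., ephedrine, phenylephrine and vasopressin) administered per patient". The wording there introduces a closed list, not examples, so an analyst following the plan would count those three drugs and no others.

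Section 7.2.2 (Both groups) sets out treatment when systolic pressure falls below 85 mmHg in the 15 minutes after induction:

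- Phenylephrine or ephedrine first, chosen by heart rate: "The blood pressure will be rechecked 1 minute following, and the process repeated once or twice if necessary".
- If the patient is still hypotensive after three such doses, "they will be considered to be in refractory hypotension and 0.5 Units of vasopressin will be administered".
- If pressure is still below 85 mmHg a minute later, "an additional 0.5 Units of vasopressin will be repeated once or twice as needed".
- Finally, "Persistent refractory hypotension despite the aforementioned vasopressors will be treated with 4 micrograms of intravenous norepinephrine".

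Section 10.2 says that vasopressor type and dosage are obtained from the study database. No section brings norepinephrine into the count or gives a reason for its absence.

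**The concern.** The endpoint is meant to measure how much vasopressor support each induction agent makes necessary. Section 1.1 hypothesises more profound hypotension with propofol, and section 12.2 names less vasopressor use as a potential benefit of methohexitol. A count that ends one step before the algorithm does cannot separate patients at the severe end. Someone whose pressure recovers on the last permitted vasopressin dose and someone who stays low and receives norepinephrine get the same score.

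At stake is the ratio of dose counts between arms. If norepinephrine is used disproportionately in the arm that already has more counted doses, leaving it out pulls the ratio toward 1. No other planned endpoint would report norepinephrine use by arm.

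**Working it through.** **The plan's own figure.** There is none for this endpoint. The 47 per arm in section 8.1 concerns the primary proportion. It is reproduced by the pooled-variance formula with 0.85 versus 0.55 (0.85 is my reading of a propofol rate slightly above the 0.82 in section 8.2): [1.96·√(2·0.70·0.30) + 1.2816·√(0.85·0.15 + 0.55·0.45)]² / 0.30² = (1.270 + 0.785)² / 0.09 ≈ 46.9, so 47. No vasopressor count enters it, so nothing below alters it.

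**Step 1: where the count stops (section 7.2.2).** Phenylephrine or ephedrine: one dose plus up to two repeats, 3 in all. Vasopressin: one dose plus one or two repeats, 2 or 3. Counted doses before norepinephrine: 3 + 2 = 5 or 3 + 3 = 6. The norepinephrine dose would be the 6th or 7th and scores zero. This ceiling applies to one pass. If hypotension recurs and the sequence restarts, the count can exceed 6.

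**Step 2: does norepinephrine fall in the window?** With a first dose at minute t and rechecks one minute apart, norepinephrine comes at t + 5 (3 + 2 doses) or t + 6 (3 + 3 doses). For t = 1 that is minute 6 or 7. With the full sequence it is still inside 15 minutes for t = 9 (9 + 6 = 15).

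**Step 3: effect on an arm mean.** The documents give no failure rate per dose, so I assume one. Let h be the share of an arm that starts treatment, f the probability that pressure stays low after each dose, and k the counted doses available (5 or 6). Assume one pass and one norepinephrine dose.

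- Counted mean = h(1 + f + … + f^(k−1)) = h(1 − f^k)/(1 − f)
- Uncounted mean = h·f^k
- Undercount relative to the counted mean = f^k(1 − f)/(1 − f^k); h cancels

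| f | k = 6 | k = 5 |
|---|---|---|
| 0.3 | 0.05% | 0.2% |
| 0.5 | 0.8% | 1.6% |
| 0.7 | 4.0% | 6.1% |

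For example, f = 0.7 and k = 6 gives 0.1176 × 0.3 / 0.8824 = 4.0%.

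The share of an arm reaching norepinephrine is h·f^k. With k = 6, h of 0.4 or 0.7 and f from 0.3 to 0.8, it runs from 0.03% to 18%, or about 0 to 11 of 60 patients.

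**Step 4: effect on the ratio of mean doses (k = 6).**

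| Arm with more doses (h, f) | Other arm (h, f) | Ratio as planned | Ratio with norepinephrine |
|---|---|---|---|
| 0.7, 0.5 | 0.4, 0.5 | 1.75 | 1.75 |
| 0.7, 0.7 | 0.4, 0.5 | 2.61 | 2.70 |
| 0.7, 0.8 | 0.4, 0.6 | 2.71 | 2.85 |

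In the first row more patients reach norepinephrine in the higher-dose arm (1.1% against 0.6%), yet the ratio does not move, because uncounted doses are the same fraction of counted doses in both arms. Attenuation needs norepinephrine use to be out of proportion to counted doses. In the other two rows including it raises the ratio by about 3% (2.698/2.614) and 5% (2.846/2.709).

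**The case against.** The best defence is that the definition is consistent: sections 1.3 and 8.3 name the same three drugs, and the count can be read as covering every step before final rescue. That is coherent, but the plan does not state it as a choice, and it does not match an endpoint labelled as a total.

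Second, severity is measured elsewhere. Refractory hypotension (1.3(3)) flags these patients after three doses, and duration and the area under the systolic pressure curve also pick up part of the difference. This stands, and it limits the damage. It does not close the gap, because refractory hypotension is binary and treats recovery on the first vasopressin dose and progression to norepinephrine alike.

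Third, the patients concerned already score 5 or 6, the most that one pass allows. They lose a unit at the top of the scale and are not scored low. That also stands.

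A reader might infer a larger problem in two ways. One is to take the missing dose, 1 of 7 or 14%, as the bias. That is the undercount for one affected patient on the full sequence; the effect on an arm mean or on the ratio is much smaller. The other is to conclude that the comparison is necessarily biased toward no difference. The documents do not support that: they give no rate of reaching norepinephrine in either arm, and the direction depends on how its use splits between arms.

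**Conclusion.** The omission is real and appears in both places that define the count. Followed literally, the plan scores a patient who needed norepinephrine the same as one controlled on the last vasopressin dose.

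The likely effect is small. Under the assumed failure probabilities of 0.3 to 0.7 per dose, about 0.05% to 6% relative to an arm's counted mean is missed, and the illustrative ratios change by 0% to about 5%. These figures rest on one pass through the algorithm, a constant failure probability and a single norepinephrine dose, none of which the documents establish as what will happen. If no patient reaches norepinephrine, the effect is zero. The primary endpoint needs only one hypotensive episode and is unaffected, as is the sample size. I would class this as a minor, free improvement.

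**What to change.** Add norepinephrine to the drug list in section 1.3(1) and in item (a) of section 8.3, so that every vasopressor dose given in the 15 minutes is counted. The cost is a wording change in two places, with no new data collection, since section 10.2 already draws on vasopressor type and dosage. Make the change before the data are analysed: the trial is not blinded (section 7.4.5), and a later decision on whether to count norepinephrine would be post hoc. If the sponsor prefers to keep the three-drug count, the plan should say why and report norepinephrine use by arm. This concerns only what is counted; no change to the treatment algorithm is implied.

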## 2.0 Background

### 2.1 Scientific Background and Gaps

Induction of anesthesia in patients treated preoperatively with ACEI or ARB is often associated with significant hypotension. (Rosenman et al., 2008) (Bertrand et al., 2001) One stated reason for this hypotension is the fact that antagonists of the renin-angiotensin system may reset baroreceptor function inhibiting compensatory heart rate increases in the face of hypotension. (Giudicelli et al., 1985) The intravenous induction agents, methohexitol and propofol have opposing effects on this baroreceptor function; (JW, 2011) methohexitol administration increases baroreceptor sensitivity with a resultant increase in heart rate, (Carter et al., 1986) while propofol decreases baroreceptor sensitivity in the face of induced hypotension. (Cullen et al., 1987; Ebert et al., 1992) Consistent with this, when induction of anesthesia in ASA Physical Class 1 and 2 patients was compared, methohexitol was associated with better maintenance of heart rate and blood pressure than propofol induction.(Gold et al., 1987; Price et al., 1992) Given the significant hypotension often encountered with the use of Propofol for induction in patients on ACEI or ARB therapy(Bertrand et al., 2001; Mets, 2013; Nielson et al., 2014) and the fact that there are now increasing concerns around the use of the more cardiostable induction agent etomidate,(Komatsu et al., 2013) there is a need to establish the utility of other cardiostable induction agents for use in the increasing number of patients presenting on antagonists of the renin-angiotensin system.

## **2.2 Previous Data**

None

## **2.3 Study Rationale**

This study is being instituted to determine the hemodynamic stability of induction of anesthesia with methohexitol or propofol in patients presenting for elective surgery who were receiving ACEI or ARB therapy. In addition, we wish to determine whether there are any different effects of these induction agents on circulating neurohormones relevant to hemodynamic homeostasis, namely arginine vasopressin (AVP), Angiotensin II (All), and circulating norepinephrine (NE) and epinephrine (Epi).

# **3.0 Inclusion and Exclusion Criteria**

## **3.1 Inclusion Criteria**

1. Adult patients ( $\geq 18$  years old) treated for  $\geq 6$  weeks with ACEI or ARB
2. Patients undergoing elective surgery under general endotracheal anesthesia
3. ASA Physical Class II or III
4. Surgeries anticipated to require at least 2 peripheral intravenous catheters for adequate intravenous access

## **3.2 Exclusion Criteria**

1. BMI  $>40\text{kg}/\text{m}^2$
2. Taking both ACEI and ARB
3. History of difficult intubation in the past, or having anatomic predictors of a difficult airway defined as the following
  - a. Mallampati Grade 3 or 4
  - b. Small mouth opening
  - c. Thick neck circumference ( $>40\text{cm}$ ) and/or short thyromental distance
4. Require rapid sequence induction and intubation
5. Uncontrolled baseline blood pressure (SBP  $>180$  mmHg or DBP  $>110$  mmHg) at anesthesia preoperative clinic visit
6. Contraindication to the use of propofol or methohexitol
7. Severe coronary artery disease
8. Patients scheduled for cardiac surgery
9. History of renal failure (Creatinine level  $>2$  mg/dL)
10. Non-English speaking subjects
11. Cognitively impaired adults
12. Patient is a known or suspected difficult peripheral intravenous access

## **3.3 Early Withdrawal of Subjects**

### **3.3.1 Criteria for removal from study**

1. Unanticipated difficult airway
2. Unanticipated arrhythmia occurring during or immediately following anesthetic induction
3. Unanticipated adverse effect of pre-induction drugs (lidocaine, fentanyl) or induction drugs (methohexitol or propofol).

4. Non-adherence to study protocol guidelines for practical reasons or safety reasons

### **3.3.2 Follow-up for withdrawn subjects**

Not applicable

## **4.0 Recruitment Methods**

### **4.1 Identification of subjects**

The list of patients to present to the Anesthesia Preoperative Clinic will be reviewed on a daily basis by a provider or research associate who is directly involved in this study. All ASA Physical Class II or III patients undergoing elective surgery under general anesthesia will be identified as potential study participants. Their electronic medical record (EMR) will be reviewed by one of the study physicians in order to see whether they meet the inclusion or exclusion criteria. If they are eligible for the study, a member of the study team will approach them during their Preoperative Clinic visit, to ask them whether they would be willing to participate in this study.

### **4.2 Recruitment process**

Patients will be recruited during their Anesthesia Preoperative Clinic visit. Either before or after they see a provider for their scheduled visit, they will be approached by a member of the research team who will briefly present them with the goals of the study as well as the risks/benefits, and gauge interest in participation. If the patient is interested in participating in the study, the attending anesthesiologist who will be administering general anesthesia for the planned surgery will personally obtain informed consent for participation in the research study on the day of surgery prior to surgery.

### **4.3 Recruitment materials**

No recruitment materials will be used.

### **4.4 Eligibility/screening of subjects**

Not applicable

## **5.0 Consent Process and Documentation**

### **5.1 Consent Process**

#### **5.1.1 Obtaining Informed Consent**

##### **5.1.1.1 Timing and Location of Consent**

Consent will be personally obtained by the attending anesthesiologist in the same day unit prior to their surgery.

##### **5.1.1.2 Coercion or Undue Influence during Consent**

It will be explained to the patient that research participation is voluntary. The patient will be encouraged to ask questions and it will be explained to the patient that their decision to participate or refuse to participate in the study will have no effect on their level of care.

### **5.1.2 Waiver or alteration of the informed consent requirement**

We are requesting a waiver of consent to review patients' records to determine preliminary eligibility. We will require access to patient EMR a few days prior to their Anesthesia Preoperative Clinic visit in order to ensure that they meet the inclusion criteria and not any of the exclusion criteria. Due to the complexity of the inclusion and exclusion criteria, the large number of potentially eligible patients and the limited research personnel available to obtain informed consent, we do not believe that this research can be practically conducted without a way to perform a preliminary screening of patients prior to approaching them for full consent. Furthermore, we are concerned that we will not obtain accurate enough data if we rely solely on patient answers without reviewing their medical record to assess for eligibility. If we deem that the patient is not a suitable study candidate, none of their PHI will be recorded. Performing a preliminary screening will also allow us to channel our research personnel efficiently and thus allow them to spend more time with potential study participants and to answer any potential questions they may have about inclusion in the study.

## **5.2 Consent Documentation**

### **5.2.1 Written Documentation of Consent**

Written consent will be obtained. A signed and dated copy will be retained by the patient. A signed and dated copy will also be stored in the locked office of the research team and stored in the patient's medical record.

### **5.2.2 Waiver of Documentation of Consent (Implied consent, Verbal consent, etc.)**

Not applicable as we are obtaining full written consent.

## **5.3 Consent – Other Considerations**

### **5.3.1 Non-English Speaking Subjects**

Not applicable

### **5.3.2 Cognitively Impaired Adults**

#### **5.3.2.1 Capability of Providing Consent**

Not applicable

#### **5.3.2.2 Adults Unable To Consent**

Not applicable

#### **5.3.2.3 Assent of Adults Unable to Consent**

Not applicable

### **5.3.3 Subjects who are not yet adults (infants, children, teenagers)**

#### **5.3.3.1 Parental Permission**

Not applicable

### 5.3.3.2 Assent of subjects who are not yet adults

Not applicable

## 6.0 HIPAA Research Authorization and/or Waiver or Alteration of Authorization

### 6.1 Authorization and/or Waiver or Alteration of Authorization for the Uses and Disclosures of PHI

Check all that apply:

- Not applicable, no identifiable protected health information (PHI) is accessed, used or disclosed in this study. [Mark all parts of sections 6.2 and 6.3 as not applicable]
- Authorization will be obtained and documented as part of the consent process. [If this is the only box checked, mark sections 6.2 and 6.3 as not applicable]
- Partial waiver is requested for recruitment purposes only (Check this box if patients' medical records will be accessed to determine eligibility before consent/authorization has been obtained). [Complete all parts of sections 6.2 and 6.3]
- Full waiver is requested for entire research study (e.g., medical record review studies). [Complete all parts of sections 6.2 and 6.3]
- Alteration is requested to waive requirement for written documentation of authorization (verbal authorization will be obtained). [Complete all parts of sections 6.2 and 6.3]

### 6.2 Waiver or Alteration of Authorization for the Uses and Disclosures of PHI

#### 6.2.1 Access, use or disclosure of PHI representing no more than a minimal risk to the privacy of the individual

##### 6.2.1.1 Plan to protect PHI from improper use or disclosure

Information is included in the "Confidentiality, Privacy and Data Management" section of this protocol.

